### **6.2.1. Aim 2 Analysis: Hidden Markov Model for Infection Prevalence**

The primary analysis for Specific Aim 2 will be a hidden Markov model, conducted at the community level using a truncated normal distribution. Analyses will be conducted in the continuation and stopping arms separately, as distribution of azithromycin likely affects the relationship between the indicators. This will allow for understanding of the best tools for surveillance both with and without azithromycin treatment. This model will use four diagnostic tests – TF, TI, ocular chlamydia, and seropositivity to CT694 and Pgp3 separately, and will not assume that any of the tests are a gold standard. The truncated normal distribution allows several options to handle the expected high density of communities with zero prevalence, including zero-inflation or a free fitted parameter. The model will incorporate delays in TF and serology, as TF follicles can take months or longer to recede and serologic measurements are long-lasting. The hidden Markov model will be fit to the prevalence of the indicators for trachoma transmission to estimate the prevalence of the true hidden prevalence of trachoma. For the test of treatment, we will assess the effect of continuation versus stopping on alternative indicators alone and in combination. Absence of an effect of treatment will suggest that there is no true infection in the community. In practice, we have found some degree of model exploration necessary, and our publications will include all explored models. Estimation will be conducted using the standard Metropolis algorithm (as we have conducted before).

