4.1.2 MONITORING ELIGIBILITY

Monitoring will be based on population-based samples. The following groups will be monitored at each study visit: 1) a random sample of 50 children aged 0-9 years will receive conjunctival photography and swabbing; 2) a random sample of 40 children aged 1-9 years will receive dried blood spot collection. Eligibility for these groups will be based on the previous census.

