### 2.2. Objectives

**Specific Aim 1.** Determine if local elimination of ocular *Chlamydia trachomatis* can be achieved in the absence of azithromycin intervention.

*We hypothesize that stopping mass azithromycin in communities with up to 20% prevalence of TF will be non-inferior to continuation of annual mass azithromycin at 36 months.*

**Specific Aim 2.** Assess ongoing true transmission of infection in low TF areas by evaluating alternative indicators.

*We hypothesize that alternative indicators can supplement or even replace TF, and that the 95% confidence interval of the estimate for true infection from a hidden Markov model including alternative indicators of transmission will include zero (elimination).*

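### Aim 2 fits a truncated normal to community prevalences with no stated link to number positive out of number tested, so zero-inflation applied to observed prevalence could count sampling zeros as true zeros

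*SAP*

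**What the plan says.** SAP 6.2.1 (Aim 2 Analysis) makes a hidden Markov model the primary analysis for Aim 2, "conducted at the community level using a truncated normal distribution", with each arm analysed separately. The data entering it are community prevalences: "The hidden Markov model will be fit to the prevalence of the indicators for trachoma transmission". The target is a latent quantity, since the model is meant "to estimate the prevalence of the true hidden prevalence of trachoma", and the section says that it "will not assume that any of the tests are a gold standard". On the many zeros that it expects, it says: "The truncated normal distribution allows several options to handle the expected high density of communities with zero prevalence, including zero-inflation". The full list of options reads "including zero-inflation or a free fitted parameter", and none is selected. It does not say whether the zeros it has in mind are observed or hidden prevalences.

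The prevalences are proportions from small samples. Under Protocol 4.1.2, in each community "a random sample of 50 children aged 0-9 years will receive conjunctival photography and swabbing", and 40 children aged 1-9 years give dried blood spots. Neither document states how these denominators enter the Aim 2 likelihood.

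**The concern.** A community with no positive swab among 50 children may be free of infection, or may have low-level infection that the sample missed. A likelihood for counts keeps these two explanations apart, because it knows how often a sample of 50 misses infection at a given prevalence. A continuous density on the observed proportion does not know this. If a point mass at zero is added to that density, every observed zero is assigned to the point mass.

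The normal form has a second weakness. The sampling variance of a proportion depends on the prevalence and on the number tested, and the number tested differs between swabs or photographs (50) and blood spots (40). The plan gives no variance term that reflects either.

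Aim 2 asks whether true infection is compatible with zero in communities selected for low prevalence. That is where sampling zeros are most common and where an error in handling them would push the answer toward elimination.

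**Working it through.** **Inputs.** 50 swabbed and 40 blood-spot children per community (Protocol 4.1.2, 8.7, 8.9). 40 communities per arm (Protocol 2.3.3), arms fitted separately (SAP 6.2.1, Aim 2). The documents give no expected infection prevalence for this purpose, so 1%, 2% and 3% are assumed, with between-community SDs of 0.8, 1.5 and 2 percentage points. SAP 3.3.2 uses 5% positivity and SAP 3.3.1 an SD of 0.05; these serve as a cross-check.

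**The plan's own figure.** The Aim 2 analysis section states no number. The only Aim 2 figures are in SAP 3.3.2: 100 positives plus 1,900 negatives = 2,000 = 40 × 50, that is, one arm. The sensitivity margin is 1.96 × √(0.95 × 0.05/100) = 4.3% (4.2% stated). The specificity margin is 1.96 × √(0.95 × 0.05/1,900) = 0.98%, not the stated 0.1%. That is a separate matter with no bearing on this point.

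**Step 1: chance of an all-negative sample**, P(0/n) = (1 − p)^n.

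| True prevalence | 0/50 | Communities of 40 | 0/40 |
|---|---|---|---|
| 1% | 0.99^50 = 61% | 24 | 67% |
| 2% | 0.98^50 = 36% | 15 | 45% |
| 3% | 0.97^50 = 22% | 9 | 30% |

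The exact two-sided 95% upper limit after 0/50 is 1 − 0.025^(1/50) = 7.1%; after 0/40 it is 8.8%.

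**Step 2: let prevalence vary between communities.** Take a beta distribution with mean m and SD s: k = m(1 − m)/s² − 1, a = mk, b = (1 − m)k, and P(0/50) = B(a, b + 50)/B(a, b). This distribution has no mass at zero, so the true zero share is 0%. At means of 1%, 2% and 3% with the SDs above, P(0/50) = 65%, 45% and 31%. At mean 5% and SD 0.05 (a = 0.9, b = 17.1) it is 29%. Much of the expected pile of zeros can therefore arise from sampling alone.

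**Step 3: put a point mass on observed zeros.** Let w be the zero share and z the number of observed zeros among 40. Zeros contribute w and non-zeros contribute (1 − w) times a density, so the likelihood is proportional to w^z(1 − w)^(40 − z), maximised at w = z/40. The fitted zero share equals the observed one, about 65%, 45% and 31%, against a true 0%. This holds by construction, for one indicator at one visit with no hidden layer.

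**Step 4: fit counts instead** (simulated data, 40 communities × 50 children, same settings).
- Beta-binomial without a zero class: estimated means 1.0%, 2.0% and 3.1%.
- Beta-binomial with a zero class: median false zero share about 20%, 7% and 4% in one set of fits, 4.5%, 3.5% and 5.5% in a second maximised over a grid, and 17%, 3% and 1% in a third. In the grid fits the mean was 16%, 11% and 10%, and the median upper 95% profile limit was 60%, 43% and 34%. The medians shift with the fitting routine because the likelihood is flat in this parameter.
- Zero-inflated binomial with one common prevalence: median false zero share 28%, 24% and 18%. Counts alone are not enough; prevalence must also vary between communities.

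**Step 5: precision.** √(p(1 − p)/50) is 1.4 points at p = 1% and 3.1 points at p = 5%. With 40 children it is √(50/40) = 1.12 times larger.

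**The case against.** A reader might infer that the plan treats each 0/50 as a true zero and that Aim 2 will therefore find elimination where infection persists. The documents do not support that. Zero-inflation is one of at least two options and none is selected; the free-parameter option is untested here. The model has a hidden state, treats no test as definitive, combines PCR with TF, TI and serology, and allows for delays in TF and serology. A PCR zero need not force the hidden prevalence to zero. The zeros in question may even be hidden ones, in which case zero-inflation would sit where it belongs.

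It is also fair to say that the illustration is not the planned model, that its zero share follows by construction, and that the modelling papers cited by the SAP, not available here, may define an observation layer. Aim 2 does not drive the sample size or the randomized comparison, and the SAP promises to publish all explored models.

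These points limit the claim to what one permitted implementation could do. They do not supply the missing layer: as written, all the indicators enter as prevalences from 40 to 50 children. Publishing every explored model also does not fix in advance which one is primary.

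**Conclusion.** The point holds as a fault in how the observation model is specified, with a concrete better alternative. It is not a demonstrated bias in the final Aim 2 result. The chances of 0/50 and 0/40 are exact for independent sampling from a large community. The 65%, 45% and 31% apply only if zero-inflation is placed on observed prevalence, and rest on the assumed means, SDs and beta form.

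A count likelihood would reduce the risk of false elimination without removing it. SAP 2.2 reads a 95% interval for true infection that reaches zero as elimination, and SAP 6.2.1 (Aim 2) takes no treatment effect as a sign of no infection. Both reward imprecision under any likelihood: a single community at 0/50 has an exact interval of 0 to 7.1%, which still includes zero.

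The change should be made, because Aim 2 concerns hidden infection near zero and the remedy is cheap. The Aim 1 comparison is unaffected.

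**What to change.** In SAP 6.2.1 (Aim 2 Analysis), before unmasking:

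1. Model the number positive given the number tested, for each indicator, as beta-binomial or as binomial given a hidden prevalence that varies by community. Do not use a binomial with one common prevalence. This replaces the truncated normal on observed prevalences.
2. Drop zero-inflation of observed prevalences. If a structural-zero state is wanted, place it on the hidden prevalence only, name it as the primary choice, and report the interval for its share as well as the estimate, because that share is weakly identified even with counts.
3. State that the interval and no-effect rules are separate sources of false elimination, to be addressed in their own right.

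The cost is SAP wording and some added likelihood code; the Metropolis algorithm already planned can fit it. The downside is a wider and less favourable statement about zero prevalence.

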### **6.3. Missing data**

Complete case analysis. We propose to analyze only the existing data. In the case of data missing from an entire community, we will simply compute the test statistic (linear model) with the available communities, conducting the permutation test with all communities. Communities with missing outcomes are still able to receive randomization allocations during the test. This would be the primary analysis reported.

Sensitivity analysis. In the event of missing outcomes for entire communities, we will assign values to the missing communities and determine how extreme the missing values would need to be for the overall conclusions to change. We will conduct this analysis by assigning the purported value, and repeating the statistical test procedure, for a range of purported values.

## **6.4. Additional analyses**

For the primary analysis in Aim 1 that compares arms, transformations to improve heteroskedasticity and normality may be undesirable in this case, since the noninferiority margin is more interpretable on an absolute risk scale. If we have concerns about the appropriateness of the model assumptions for a community-level analysis, we will consider as an alternative a logistic regression of individual level outcomes to model the probability of infection conditional on arm and community-level baseline prevalence, with marginal standardization to estimate differences in prevalence between arms. In this alternative analysis, we would estimate a 95% confidence interval of the difference using a non-parametric bootstrap that resamples communities with replacement and uses the 2.5% and 97.5% percentiles of the bootstrap distribution.

## **6.5. Harms**

Passive reporting of symptoms has been used in the past for azithromycin trials. More than 800 million doses have been distributed as part of the trachoma program, and this study will be unlikely to unveil new side effects. We intend to be vigilant, and serious adverse events suspected of being drug-related will be reported to the DSMC and to ITI within 24 hours of our notification.

## **6.6. Statistical software**

We plan to use R statistical software (version 3.6 or later) for all analyses.

## 8. Revision history

Version	Date	Summary of Changes, Justification, and Timing vis-à-vis key trial events (enrollment completion, interim analyses, unmasking, etc)
1	2020-03-04	
 
First version adapted from the SAP developed for the NIH grant application.
 

2	2020-03-20	
 
Changed “discontinuation” arm label to “stop” label to make it more clear.
 

